Aim 3: Demonstrate target engagement by measuring BOLD responses evoked by TMS pulses to the right dIPFC during threat of shock.

Number of Subjects 75

**Main Inclusion
and Exclusion
Criteria**

Healthy volunteers, between 18 – 50 years old, free of psychological and neurological conditions, free of contraindications for TMS and MRI

Aim 1: Outcome measures. Fear potentiated startle (FPS) and Anxiety potentiated startle (APS) Statistical Analysis. The main analysis will be a 3 [stimulation: pre-stimulation vs. post-active vs. post-sham] by 2 [protocol: cTBS vs. iTBS] repeated-measures ANOVA.

**Statistical
Methodology**

Aim 2: Outcome measures. Accuracy and reaction time during the Sternberg Working memory paradigm. Statistical Analysis. The main analysis will be a 3 [stimulation: pre-stimulation vs. post-active vs. post-sham] by 2 [protocol: cTBS vs. iTBS] repeated-measures ANOVA.

Aim 3: Outcome measures. TMS-evoked BOLD activity during periods of acute fear and sustained anxiety. Statistical Analysis. BOLD maps will then be analyzed using a paired-sample t-test to compare BOLD responses evoked by active TMS and those evoked sham scalp stimulation.

**Data and Safety
Monitoring Plan**

The Principal Investigator is responsible for detecting, documenting, and reporting unanticipated problems (UPs), adverse events (AEs), including serious adverse events (SAEs), and deviations in accordance with IRB requirements and federal regulations.

CONFIDENTIAL

BACKGROUND AND STUDY RATIONALE

This study will be conducted in full accordance all applicable University of Pennsylvania Research Policies and Procedures and all applicable Federal and state laws and regulations including [as applicable include the following regulations as they apply 45 CFR 46, 21 CFR Parts 50, 54, 56, 312, 314 and 812 and Good Clinical Practice. All episodes of noncompliance will be documented.

Introduction

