This research is significant because upon completion, we expect to have direct evidence for a causal role of the right dIPFC in anxiety regulation, complete with evidence

CONFIDENTIAL

of target engagement through simultaneous TMS/fMRI, and a novel application to anxiety. This research will lay the groundwork for my long-term career objective, which is to develop an independent, NIH-funded research program employing psychophysiology, neuroimaging, and neuromodulation in healthy and anxious participants aimed at developing a circuit-level understanding of the neurobiological mechanisms underlying anxiety.

2 Study Objectives

Aim 1: Determine the effect of a 1-week course of TBS treatment (Continuous vs. Intermittent; right dlPFC target) on anxiety using the unpredictable shock-threat paradigm. Our hypothesis, consistent with our pilot data, is that strengthening circuits in the right dlPFC will facilitate anxiety regulation. Accordingly, we expect excitatory but not inhibitory TBS (compared to sham) to reduce induced anxiety.

Aim 2: Determine the effect of a 1-week course of TBS treatment (Continuous vs. Intermittent; right dlPFC target) on anxiety-related WM-deficits using the Sternberg WM paradigm during threat of shock. Our hypothesis is that the rTMS will strengthen right dlPFC circuits, which will rescue the anxiety-related WM deficits. Accordingly, we expect that 10 Hz rTMS (compared to sham) will improve accuracy on the Sternberg WM task during threat.

Aim 3: Demonstrate target engagement by measuring BOLD responses evoked by TMS pulses to the right dlPFC during threat of shock. Our hypothesis is that direct stimulation of the right dlPFC will reduce ongoing anxiety-related activity. Accordingly, we expect active but not sham TMS pulses to the right dlPFC to evoke BOLD deactivations in regions of the fear/anxiety network (i.e. amygdala, BNST, anterior insula).

3 Investigational Plan

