3.2 Study Endpoints

Aim 1: Determine the effect of a 1-week course of rTMS TBS treatment (Continuous vs. Intermittent; right dIPFC target) on anxiety using the unpredictable shock-threat paradigm. Our hypothesis, consistent with our pilot data, is that strengthening circuits in the right

CONFIDENTIAL

dIPFC will facilitate anxiety regulation. Accordingly, we expect excitatory but not inhibitory TBS (compared to sham) to reduce induced anxiety.

Aim 2: Determine the effect of a 1-week course of rTMS TBS treatment (Continuous vs. Intermittent; right dIPFC target) on anxiety-related WM-deficits using the Sternberg WM paradigm during threat of shock. Our hypothesis is that the rTMS will strengthen right dIPFC circuits, which will rescue the anxiety-related WM deficits. Accordingly, we expect that iTBS (compared to sham) will improve accuracy on the Sternberg WM task during threat.

Aim 3: Demonstrate target engagement by measuring BOLD responses evoked by TMS pulses to the right dIPFC during threat of shock. Our hypothesis is that direct stimulation of the right dIPFC will reduce ongoing anxiety-related activity. Accordingly, we expect active but not sham TMS pulses to the right dIPFC to evoke BOLD deactivations in regions of the fear/anxiety network (i.e. amygdala, BNST, anterior insula).

4 Study Population and Duration of Participation

Participants will be recruited without any preference based on gender, race, religion, or other social variables, and participants will not be excluded on the basis of sex/gender, racial, or ethnic affiliation. We exclude pregnant women because of the unknown effects of the TMS pulses, shocks, and fMRI on the developing fetus. We exclude non-English speakers since not all the instruments and tests we use are translated and validated in Spanish or other languages.

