5.1.9 Procedures

TMS motor threshold testing: The resting motor threshold (MT) will be determined in order to find the safe TMS dosing level. MT is defined as the minimum magnetic flux needed to elicit a threshold EMG response in a target muscle in 5 out of 10 trials. MT is the standard in the field for measuring cortical excitability and to reduce seizure risk. MEPs for the contralateral first dorsal interosseus (FDI) muscle will be measured with EMG. The scalp region producing the largest amplitude MEP will be identified. At that scalp location, the lowest TMS intensity able to elicit 5 MEP's of $\geq 50\mu\text{V}$ in peak-to-peak amplitude in 10 trials at this site will be determined using a descending method of limits procedure.

Sternberg working memory task: On each WM trial, subjects will see a series of 4 letters presented singularly (encoding period) that will be followed by a brief interval where subjects are required to maintain these letters (maintenance period). At the end of the maintenance period, subjects will be prompted to make a response based on the task instructions (response period; Sternberg, 1966). The response prompt will consist of a letter and a number. The letter will be chosen from the study series, and the number will correspond to a position in the series. The subjects will indicate whether the position of the letter in the series matches the number.

There will be 2, 14 min runs of the experiment. Within each run, there will be 4 blocks (2 threat, 2 safe). Within each block, there will be 2 types of trials based on the delivery of startle probes. On each trial a startle probe will be presented either during the maintenance period or the ITI. There will be 6 trials per condition per block. There will be a total of 3 shocks per run presented at random points during the threat blocks.

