6.1 Primary Endpoints

Aim 1: Determine the effect of a 1-week course of TBS treatment (Continuous vs. Intermittent; right dlPFC target) on anxiety using the Neutral, Predictable, and Unpredictable (NPU) shock-threat paradigm.

Outcome measures. Fear potentiated startle (FPS) will be calculated by subtracting the blink magnitude during the predictable inter-trial interval (ITI) from the predictable cue. Anxiety potentiated startle (APS) will be calculated by subtracting the blink magnitude during the neutral ITI from the unpredictable ITI. Online anxiety ratings will be processed similarly.

Statistical Analysis. The main analysis will be a 3 [stimulation: pre-stimulation vs. post-active vs. post-sham] by 2 [protocol: cTBS vs. iTBS] repeated-measures ANOVA. In addition to the main factors considered, we may also co-vary out several individual difference measures (e.g. baseline anxiety via self-report questionnaires, counterbalance order, overall stimulation accuracy, and Sternberg working memory (WM) performance to assess target engagement).

Aim 2: Determine the effect of a 1-week course of TBS treatment (Continuous vs. Intermittent; right dlPFC target) on anxiety-related WM-deficits using the Sternberg WM paradigm during threat of shock.

Outcome measures. During each Sternberg trial, subjects will see a series of 5 or 8 letters presented singularly (encoding period) that will be followed by a brief interval where subjects are required to maintain these letters (maintenance period). At the end of the maintenance period, subjects will indicate whether the position of the letter in the series matches the number. Accuracy will be scored as the percent correct for each trial type.

Statistical Analysis. The main analysis will be a 3 [stimulation: pre-stimulation vs. post-active vs. post-sham] by 2 [protocol: cTBS vs. iTBS] repeated-measures ANOVA. As with Aim 1, we may also include several other individual difference measures as covariates in this analysis.

Aim 3: Demonstrate target engagement by measuring BOLD responses evoked by TMS pulses to the right dlPFC during threat of shock.

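### The Aim 2 main analysis has no threat-versus-safe term, so it cannot tell rescue of the anxiety-related working-memory deficit from a general working-memory gain

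*Combined protocol and SAP*

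**What the plan says.** Section 6.1 states Aim 2 as the effect of theta-burst stimulation "on anxiety-related WM-deficits using the Sternberg WM paradigm during threat of shock". The hypothesis in sections 2 and 3.2 is that stimulation will strengthen right dlPFC circuits, "which will rescue the anxiety-related WM deficits". The prediction in section 3.2 is narrower: "we expect that iTBS (compared to sham) will improve accuracy on the Sternberg WM task during threat".

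The outcome in section 6.1 is "Accuracy will be scored as the percent correct for each trial type". The main analysis is a repeated-measures ANOVA with stimulation (pre-stimulation, post-active, post-sham) and protocol (cTBS, iTBS) as its only factors. Individual-difference covariates are optional. The Study Summary gives the same model and lists the outcomes as "Accuracy and reaction time during the Sternberg Working memory paradigm".

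The task collects both conditions. Section 5.1.9 says "Within each run, there will be 4 blocks (2 threat, 2 safe"), with two runs per visit, and "There will be 6 trials per condition per block".

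Aim 1 uses the same ANOVA, but section 6.1 first turns its outcomes into contrasts. For example, "Anxiety potentiated startle (APS) will be calculated by subtracting the blink magnitude during the neutral ITI from the unpredictable ITI".

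**The concern.** A deficit caused by anxiety is the shortfall in accuracy under threat relative to safety. To show that stimulation rescues it, the analysis must show that the shortfall shrinks. Aim 1 builds the corresponding subtraction into its outcome before the ANOVA; Aim 2 has no such step and no condition term in the model.

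The plan also does not say whether threat blocks, safe blocks or both supply the accuracy score. Trial type does not settle this: section 6.1 does not define it, and section 5.1.9 describes two types of trial by startle-probe timing (maintenance period or inter-trial interval), not by threat or safety.

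At stake is the interpretation of a positive Aim 2 result. Stimulation is given during the Sternberg task so as to enhance its effect (section 5.1.9), so a gain in working memory regardless of threat is a realistic alternative to rescue.

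**Working it through.** **Structure.** Let T and S be a subject's active-minus-sham change in accuracy in threat and safe blocks. Rescue means that T exceeds S. The possible inputs to the stated ANOVA are:

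- Threat blocks only: tests T. Positive if T = S > 0 (general gain, deficit unchanged) and if T > S = 0 (rescue).
- Threat and safe pooled: tests (T + S)/2. It responds more strongly to a general gain than to rescue of the same size.
- Safe-minus-threat score: tests the change in the deficit. This is the only one of the three that is null under an equal gain, and it is not in the plan.

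**Inputs from the plan.** Section 6.2 gives 26 per group and two-tailed alpha 0.025, with f = 0.5 and power 0.8. The 26 can be reproduced: a fixed-effects F test with 2 numerator df, six cells and noncentrality f²N needs N = 51, or 26 per group after rounding up. Section 6.2 sizes a main effect only.

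**Assumed inputs, not in the plan.** T and S each have SD 1, with correlation r. Effects are in these SD units and occur in the iTBS group only.

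**Formulas.** Two-group t-test, df = 50, noncentrality d√(26/2) = 3.606d, critical |t| = 2.311.

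- Threat only: d = effect in threat blocks.
- Pooled: d = mean effect / √((1 + r)/2).
- Difference: d = (threat effect − safe effect) / √(2(1 − r)).

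**General gain, equal in threat and safe: probability of rejection**

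| Gain | Threat only | Pooled, r = 0.3 / 0.5 / 0.7 | Difference |
|---|---|---|---|
| 0.5 | 0.314 | 0.475 / 0.416 / 0.369 | 0.025 |
| 0.8 | 0.716 | 0.894 / 0.843 / 0.790 | 0.025 |
| 1.0 | 0.898 | 0.983 / 0.965 / 0.942 | 0.025 |

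Example: for gain 0.8 and r = 0.3, pooled d = 0.8/√0.65 = 0.992, giving 0.894.

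Simulating the stimulation × protocol term of the 3 × 2 ANOVA itself (20,000 runs per cell, independent visit errors, gain of 0.8 only at the iTBS post-active visit) gives about 0.77 for threat only, 0.933 / 0.889 / 0.839 for pooled and 0.024 / 0.025 / 0.026 for the difference.

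These are rates of misattribution, not type I errors: accuracy really has changed, and only the label is wrong.

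**Rescue confined to threat blocks, 0.8 SD.** Threat only has power 0.716. Pooled d = 0.4/√((1 + r)/2) = 0.496 / 0.462 / 0.434, power 0.310 / 0.268 / 0.237 at r = 0.3 / 0.5 / 0.7. The choice of blocks that the plan leaves open therefore matters.

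**Power of the missing test (difference score)**

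| Effect (threat, safe) | r = 0 | 0.3 | 0.5 | 0.7 |
|---|---|---|---|---|
| 0.8, 0 | 0.400 | 0.554 | 0.716 | 0.917 |
| 0.8, 0.4 | 0.107 | 0.146 | 0.202 | 0.335 |

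**A second set of assumptions.** A separate simulation used 28 per group, accuracy of 80% under threat and 85% under safe, SDs of 8 (subject), 5 (visit) and 6 (cell), and a gain of 5 points after active iTBS (4,000 runs, stimulation × protocol term). With a general gain it rejected 40% pooled, 28% threat only and 2.8% on the difference. With rescue it rejected 10%, 29% and 23%. The levels differ from those above, but the pattern is the same: threat-only accuracy responds about equally to both scenarios (28% and 29%).

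**The case against.** The strongest reply is that section 3.2 reduces Aim 2 to accuracy during threat, and the aim itself refers to threat of shock. A 3 × 2 ANOVA on threat-block accuracy tests that prediction. This stands. No passage says that threat and safe accuracy will be averaged, so the pooled figures describe a reading the plan leaves open, not one it adopts. But the hypothesis in the same section goes further, to rescue of the deficit, and threat-block accuracy alone cannot support that.

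Second, the percentages rest on assumed effects and correlations. They do: for threat-only accuracy under a general gain they run from 28% to 90% across the values tried. They should not be cited as properties of this trial.

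Third, the condition interaction may be weak. It has less power than threat-block accuracy when r is below 0.5, and very little if safe accuracy improves half as much. Section 6.2 does not size it. This is a real cost and shapes the recommendation.

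Fourth, an interaction on percent correct depends on scale. With assumed accuracies of 85% under threat and 95% under safe, an equal gain of 0.5 logits is +5.3 and +1.9 points, so a general gain near the ceiling could look like rescue. The 2.5% in the tables assumes additive normal data. This calls for a sensitivity analysis; it does not restore the stated model.

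Finally, the safe blocks could simply be analysed later. The data allow it, but choosing the blocks or the contrast after seeing results is what a stated main analysis should prevent.

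**Conclusion.** The concern holds, as something that should be fixed. As written, the Aim 2 main analysis has no threat/safe term and no difference score, and does not name the blocks. A positive result would support better accuracy under threat, or better accuracy overall, but not by itself rescue of the anxiety-related deficit.

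That conclusion is structural and needs no assumed value. Its illustrated size, a 72% chance that a general gain of 0.8 SD gives a positive threat-only result against 2.5% on the difference score, rests on the assumed effect, equal gains in both conditions and additive normal data. The limitation lies in the stated analysis, not in the data.

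**What to change.** In section 6.1 and the Study Summary:

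1. Define trial type and state which blocks enter each Aim 2 analysis.
2. Keep threat-block accuracy as the named test of the section 3.2 prediction.
3. Add condition (threat versus safe) as a within-subject factor for accuracy and reaction time. Prespecify the protocol × stimulation × condition test, with post-active versus post-sham as the contrast of interest. The pre-stimulation visit always comes first, and counterbalancing protects only active versus sham, so practice would load on the three-level stimulation main effect.
4. Claim rescue only if the condition interaction supports it, and acknowledge that this test may be underpowered.
5. Add a sensitivity analysis for the ceiling on percent correct, for example on the logit scale.

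The cost is SAP wording; no new data or visits are needed. If condition in section 5.1.9 means probe type, each visit already yields 2 runs × 2 blocks × 2 probe types × 6 trials = 48 threat and 48 safe trials. The price is the interaction's lower power when r is below 0.5, which is why it should govern the rescue claim and not replace the threat-block test.

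Separately, reconcile the set size: section 5.1.9 gives 4 letters, section 6.1 gives 5 or 8.

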3.1 General Design

Aims 1 and 2 of this project will be tested using a between-subjects design where 1 group of healthy volunteers will receive 4-day courses of active and sham cTBS stimulation to the right dlPFC, while the other group will receive 4-day courses of active and sham iTBS stimulation to the right dlPFC. In Aim 1, we will test the effects of this stimulation on anxiety during the NPU threat task. In Aim 2, we will test the effects of this stimulation on anxiety-related WM deficits using the Sternberg WM paradigm. In addition, we will also administer several self-report questionnaires to assess their baseline (pre-stimulation) anxiety. Subjects will be randomly assigned to groups, and the order of stimulation (active vs. sham) will be counterbalanced across subjects. Aim 3 will be tested using a within-subjects design where this same group of subjects will receive single-pulse active and sham stimulation to the right dlPFC during the NPU threat task while in the MRI scanner. BOLD activity to the TMS pulses will be the primary outcome measure.

Subjects will undergo 12 study visits spaced over a 4-week period (Figure 3). Subjects may also be offered an optional 13th visit where TMS/fMRI is conducted. On Week 1,

CONFIDENTIAL

subjects will undergo a pre-stimulation behavioral visit where they complete the NPU threat task and the Sternberg WM paradigm, and a pre-stimulation MRI visit where they undergo all the structural and functional imaging needed to identify the optimal target of stimulation for the course of TMS used in Aims 1 and 2. This information will be used to perform neuronavigation during the study visits to ensure accurate target stimulation. Subjects will complete the TMS/fMRI scans needed for Aim 3 during the optional visit. On Weeks 2 and 4, subjects will undergo 5 visits. The first 4 visits will be stimulation visits where they receive either active or sham stimulation while doing the Sternberg WM task. On the 5th visit, they will return for the post-stimulation test visit, where they will complete the NPU threat task and the Sternberg WM paradigm.

[figure not shown]

Figure 3: Timeline showing subject visits in the proposed project.

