iTBS. Subjects will receive 20 trains of triplet 50 Hz bursts, repeated at 5 Hz; 2 s on and 8 s off for a total of 600 pulses per session and a total duration of 3 min. and 9 s). Stimulation will occur while subjects are doing the Sternberg WM paradigm, which should facilitate the efficacy of the stimulation by taking advantage of the cognitive paired-associate stimulation (C-PAS) principle (Luber et al., 2017). The timing of the Sternberg task will be jittered so that each rTMS train will be administered during the maintenance interval of a WM trial.

Basic scans: During the MRI visit, we will collect at T1, a T2, and a diffusion-weighted echo-planar image using an available 3T scanner. Next subjects will undergo a two runs of the Sternberg task, without shocks, probes, or TMS pulses to serve as functional localizers to identify a dIPFC. Subjects may also undergo a resting state scan.

NPU TMS/fMRI. A Magventure MagPro 100X stimulator with a MRi-B91 figure-8 coil will be used. The TMS coil will be placed on the head over the target. TMS intensity will be 100% of the motor threshold (MT). For sham stimulation, a 4 cm spacer will be placed between the subject's scalp and the TMS coil. As with the study visits, subjects will have Neutral, Predictable, and Unpredictable periods. During the neutral periods, they will be safe from shocks. During the predictable periods, they can receive shocks but only when there is a cue present. During the unpredictable periods, they will be at risk for shock during the entire duration of the block. Rather than probing their ongoing fear and anxiety with the startle probes, we will replace the startle probes with single TMS pulses to the right dIPFC. This will allow us to causally examine the effect of right dIPFC activity (induced by the TMS pulse) on the neural activity that mediates fear (during the predictable cue) and anxiety (during the unpredictable cue and ITI). Importantly, by replacing the startle probes with TMS pulses, it will be possible to directly compare the TMS-evoked BOLD responses to the pattern of startle responses collected during the MRI/pre-stimulation visit. Subjects will have 1 run of active stimulation and one run of sham stimulation. Subjects may receive an additional 1 run of active stimulation at a control site in over the parietal cortex.

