Outcome measures. Standard Multi-echo fMRI preprocessing will be conducted using the AFNI software package. Steps include: slice-time correction, despiking, volume registration, TE-dependent ICA denoising (to remove non-BOLD artifacts), masking, blurring, scaling, motion scrubbing, T1-EPI alignment, normalization (using MNI template). At the first level, variable duration mini-blocks will be used to model BOLD activity during the maintenance interval of the Sternberg trials. Motion parameters and all other events will be included in the model as regressors of no interest.

Statistical Analysis. Whole-brain maps will be created for contrasts mirroring those used to create FPS and APS in Aim 1. FP-BOLD and AP-BOLD maps will then be analyzed using a paired-sample t-test to compare BOLD responses evoked by active TMS and those evoked sham scalp stimulation. Monte Carlo simulations will be conducted to cluster-correct the results using a voxelwise p-value threshold of 0.001, a cluster alpha of 0.05, and a realistic spatial autocorrelation function to model the noise. This is the standard approach implemented in AFNI following the influential Eklund et al. 2016 paper. As with Aim 1, we may also include several other individual difference measures as covariates in this analysis.

CONFIDENTIAL

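### The only first-level fMRI model given for Aim 3 is for Sternberg maintenance intervals, which do not occur in the Aim 3 runs, and read literally it makes the TMS pulse a nuisance event

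*Combined protocol and SAP*

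**What the plan says.** Section 6.1 (Primary Endpoints) describes the Aim 3 analysis in two steps.

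- **First level.** After preprocessing, "variable duration mini-blocks will be used to model BOLD activity during the maintenance interval of the Sternberg trials". The next sentence adds: "Motion parameters and all other events will be included in the model as regressors of no interest". No other first-level model appears in the document.
- **Group level.** "Whole-brain maps will be created for contrasts mirroring those used to create FPS and APS in Aim 1". The resulting FP-BOLD and AP-BOLD maps go into a paired t-test of active against sham TMS, with cluster correction (voxelwise threshold 0.001, cluster alpha 0.05).

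The outcome itself is stated twice elsewhere. The Study Summary gives it as "TMS-evoked BOLD activity during periods of acute fear and sustained anxiety", and section 3.1 says that "BOLD activity to the TMS pulses will be the primary outcome measure".

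On acquisition, section 3.1 states: "Subjects will complete the TMS/fMRI scans needed for Aim 3 during the optional visit". Section 5.1.7 lists one procedure for that visit, NPU TMS/fMRI. For those runs section 5.1.9 says "we will replace the startle probes with single TMS pulses", and it plans one active and one sham run, with a possible further active run over a parietal control site. The Sternberg task is scanned at the separate basic MRI visit, as "two runs of the Sternberg task, without shocks, probes, or TMS pulses to serve as functional localizers".

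**The concern.** The first-level sentence describes a different experiment from the one that yields the Aim 3 data. It takes Sternberg maintenance as the effect to estimate, whereas the Aim 3 runs use the NPU task and the response of interest is to a TMS pulse. The companion sentence on other events then covers the pulses and makes them terms of no interest.

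Aim 3 sits under Primary Endpoints and is the study's evidence of target engagement. An analyst cannot apply the stated model to these runs. The analyst must replace it with one that the plan does not give, choosing the pulse regressors, the nuisance terms and the treatment of pulses that fall outside the two contrasts. If those choices are made after the data have been seen, the group test and its cluster correction are prespecified but the maps that enter them are not.

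**Working it through.** The plan has no figure to reproduce here. The check sets the model against the data it must fit and the contrasts it must feed.

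**Step 1. Does the modelled event occur in the Aim 3 runs?** (sections 5.1.7 and 5.1.9)

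| Scanned runs | Number per subject | Sternberg maintenance intervals | TMS pulses | Active/sham factor |
|---|---|---|---|---|
| NPU TMS/fMRI, optional MRI visit | 1 active + 1 sham = 2 (3 with the parietal run) | none | yes | yes |
| Sternberg localizer, basic MRI visit | 2 | yes | none | no |

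The modelled event therefore occurs in 0 of 2 Aim 3 runs, or 0 of 3. A regressor with no events in a run is a column of zeros, and its coefficient cannot be estimated. The localizer runs do contain the event, but with no pulses and no active/sham factor they cannot supply the paired comparison.

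**Step 2. Which regressors do the contrasts need?** Section 6.1 (Aim 1) defines FPS as predictable cue minus predictable ITI, and APS as unpredictable ITI minus neutral ITI. Writing β for the pulse-evoked coefficient in a cell, the mirrored contrasts are:

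- FP-BOLD = β(predictable cue) − β(predictable ITI)
- AP-BOLD = β(unpredictable ITI) − β(neutral ITI)

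In the NPU task, probes fall in the cue or the ITI of three conditions (section 5.1.9). With pulses replacing probes, there are 3 × 2 = 6 possible pulse cells:

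| Condition | Cue | ITI |
|---|---|---|
| Neutral | not used | AP-BOLD (subtracted) |
| Predictable | FP-BOLD | FP-BOLD (subtracted) |
| Unpredictable | not used | AP-BOLD |

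The contrasts use 2 + 2 = 4 cells with no overlap, which leaves 6 − 4 = 2. The first-level text names none of the four as of interest. A single pooled pulse regressor would not do, because neither difference could be formed from it.

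**Step 3. What else is left open?**

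- *Unused cells.* Section 5.1.9 treats the unpredictable cue as an anxiety period alongside the unpredictable ITI, but APS uses only the ITI. The plan does not say how pulses in the unpredictable and neutral cues are to be modelled.
- *Shocks.* In the NPU task description, shocks fall in the predictable cue and the unpredictable ITI. These are the threat cells of the two contrasts; the cells subtracted from them contain none. How shocks are separated from pulse responses therefore bears on both maps. The active-sham comparison may cancel part of this, and the documents give no basis for sizing what remains.

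**The case against.** The strongest reply is that the sentence is misplaced, not wrong. It fits the Sternberg localizer runs well and may belong to them. On that reading the clause on other events never touches the TMS pulses, because the localizer runs have none, and the charge that the outcome is classed as nuisance falls away. Even on the literal reading, a regressor of no interest still yields a coefficient. The outcome is stated clearly in several places, and nobody would conclude that the sponsor means to discard the TMS response. Aim 3 also comes from an optional visit in a pilot study.

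Much of this is fair. The intent is clear, and the nuisance point depends on a literal reading. But the localizer reading is an inference, and it does not rescue the plan: the Aim 3 runs would then have no first-level model at all, and the same text would have to be added. Nuisance coefficients would give the contrasts only if pulses were entered separately by condition and period, which the plan does not say.

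A narrower objection is that the remedy goes too far in naming nuisance terms and in modelling the two unused cells. Both steps follow the plan's own rule that all other events enter as regressors of no interest. It is fair to ask whether every term will be well estimated. If the scanner runs copy the block structure of the behavioural NPU task (an assumption, since no pulse count is given for them), each cell holds 4 pulses per run: 2 blocks × 2 trials for predictable and unpredictable, and 4 blocks × 1 trial for neutral. The sponsor should check estimability when fixing the model.

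**Conclusion.** The concern holds. Followed exactly, the stated first-level model has an empty regressor of interest in every Aim 3 run and does not define the FP-BOLD and AP-BOLD contrasts required by the next paragraph.

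This is a specification error, and the estimand is not undefined: the outcome, the two contrasts, the paired test and the cluster correction are all stated and can stand. The counts show that the model and the data do not match; they do not measure an effect on the result. The conclusion rests on the optional MRI visit containing only what sections 5.1.7 and 5.1.9 list for it. It depends on no assumption about alpha, power, effect size or sample size. The text should be corrected before any Aim 3 data are examined.

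**What to change.** Replace the first-level sentence in section 6.1 (Aim 3) with a model for each NPU TMS/fMRI run:

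1. Enter TMS-pulse onsets as event regressors of interest, separately for at least the predictable cue, predictable ITI, unpredictable ITI and neutral ITI.
2. Model pulses in the unpredictable cue and neutral cue separately, so that they do not enter the baseline.
3. List the nuisance terms: cues or blocks, shocks, and motion parameters.
4. Define FP-BOLD as predictable cue minus predictable ITI, and AP-BOLD as unpredictable ITI minus neutral ITI.
5. State that the paired test compares the active and sham dlPFC runs, and that any parietal control-site run is modelled and kept separate from it.
6. Leave the planned cluster correction unchanged.
7. Confine the Sternberg maintenance model to the localizer runs.

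The cost is SAP wording and analysis code. Data collection, sample size, the group test and alpha do not change.
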